## **D2. Participant Procedures:**

**Medication administration and adherence monitoring.** *Micronized progesterone (Prometrium; 200mg)*: Progesterone is a hormone released mainly during the luteal phase of the menstrual cycle and pregnancy, and has been used for over 50 years in the treatment of various disorders including ovarian failure, premenstrual symptoms, amenorrhea, dysfunctional uterine bleeding, menopausal symptoms and for contraception (de Lignieres, 1999; Simon, 1995). Because it is poorly absorbed and has extensive first pass metabolism, several synthetic progesterone derivatives have been synthesized and marketed. However, these synthetic progesterone derivatives have additional androgenic, corticosteroid and anabolic effects and have been associated with unfavorable side effects including fluid retention, androgenic effects and alterations in lipid profile (Goodman et al., 1996). Recently, micronized progesterone formulations that can be taken orally have been developed to overcome the poor absorption of progesterone and the unfavorable side effects of the synthetic progesterone (McAuley et al., 1996; Simon, 1995). The safety, tolerability and efficacy of micronized progesterone and subjective measures have been investigated over a wide dose range, from 200 to 2,000 mg/day (Freeman et al., 1995; Gron et al., 1997; Schweizer et al., 1995). Micronized progesterone provides a specific pharmacological tool to investigate the effects of this hormone, devoid of the additional pharmacological effects that synthetic progesterone derivatives have.

Progesterone or placebo dosing will begin at 9pm on study day 1. On study days 2-4 participants will take medication at home at 9am and 9pm, and on day 5 the final dose will be taken at 9am. Capsules will be prepared by the MUSC Investigational Drug Services. Previous studies (Fox et al., 2013; Sofuoglu et al., 2001; 2011) have used twice daily administration during the follicular phase of 200mg progesterone in order to achieve stable levels of progesterone comparable to normal luteal phase levels (2-20 ng/ml). Safety and tolerability of micronized progesterone has been established in numerous studies with nicotine (Sofuoglu et al., 2001; 2011) and cocaine (Evans & Foltin, 2006; Fox et al., 2013; Reed et al., 2011 Sofuoglu et al., 2002; 2004) dependent individuals.

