Adherence Monitoring. Participants will record themselves taking their morning and evening medication doses and then submit these videos to research staff via RedCap survey. Subjects may use their personal smartphones for video submission. If they do not have a smartphone, one will be loaned to them during the course of the study, as video submissions may only be completed on a smartphone (cannot be completed on a computer). A survey link will be sent to the subject via text message twice daily. Video capture will occur as part of the RedCap survey. Videos are automatically stored on some Android smartphones, and participants will be informed of that so they can delete the files, if necessary. Participants using iPhones (and using loaner iPhones from our group) will not have stored videos on their phone and nothing will need to be deleted.

**Ovarian Hormones:** *Progesterone* and *Estradiol* will be measured from salivary samples collected using the passive drool method. Saliva samples will be collected daily; in the lab on days 1 and 5, and at home on days 2-4. Participants will be trained on how to collect and store the samples by study personnel on study day 1.

**Cannabis Withdrawal.** The *Cannabis Withdrawal Scale (CWS; Allsop et al., 2011)* will be used to assess cannabis withdrawal symptoms. CWS is a 19-item self-report measure that assesses cannabis withdrawal symptoms in the past 24 hours (sample items: I felt restless; I had a headache; I had trouble getting to sleep at night) on a 10-point Likert scale (0=Not at All to 10=Extremely). To establish a baseline withdrawal score, the CWS will be administered in person on study day 1. CWS will then be administered once on study days 1 and 5, and twice daily on study days 2-4 as part of the RedCap medication adherence survey that will be sent via text message to the participant. Participants will be asked to respond with reference to the past 12 hours.

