#### Example study day 1 timeline

Time	Procedure	Duration
9:00 am	Saliva, breathalyzer, utox	15 mins
9:15	TLFB	15 mins
9:30	Saliva sample (hormones)	5 mins
9:35	Cognitive testing	15 mins
9:50	Self-report assessments (FrSBe, CWS, PANAS-X, CUDIT-R)	20 mins
10:10	Medication instructions	20 mins
10:30	Compensate/discharge	
9:00 pm	First medication dose, CWS (at home)	

**Study days 2-4:** Participants will be prompted by RedCap to complete medication adherence and CWS at 9am and 9pm. Each day participants will schedule a Skype/FaceTime call with study personnel to conduct saliva testing and adverse event assessment. Should an adverse event occur, trained personnel will assess via video conference to determine necessary procedures. Participants will also provide a saliva sample for hormone testing. Participants will be provided with labeled tubes for saliva collection and storage. They will fill out the date and time and place in the freezer to be stored until study day 5 when they will bring to ASD clinic for testing.

**Study day 5 visit:** Participants will present to the ASD clinic by 10am for final study visit. They will undergo saliva testing, urine toxicology, Breathalyzer, and TLFB, followed by hormone saliva sampling and cognitive testing. Participants will be debriefed, compensated, and discharged.

Time	Procedure	Duration
9:00am	Last medication dose, CWS (at home)	
9:00	Saliva, breathalyzer, utox	15 mins
9:15	TLFB	15 mins
9:30	Saliva sample (hormones)	5 mins
9:35	Cognitive testing, FrSBe	15 mins
9:50	Compensate/debrief	10 mins
10:00	Discharge	

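### The Days 2-4 home hormone samples have no set time relative to dosing, so the sampling point behind the Aim 1 progesterone level is undefined

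*Combined protocol and SAP*

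**What the plan says.** All references are to the combined protocol and SAP.

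- **Dosing (D2, medication administration).** The first dose is at 9pm on Day 1, then 9am and 9pm on Days 2-4, and a last dose at 9am on Day 5. Earlier studies are said to have used this regimen "in order to achieve stable levels of progesterone comparable to normal luteal phase levels (2-20 ng/ml".
- **Hormone sampling (D2, Ovarian Hormones).** "Saliva samples will be collected daily; in the lab on days 1 and 5, and at home on days 2-4". No clock time is given.
- **Study days 2-4.** "Participants will be prompted by RedCap to complete medication adherence and CWS at 9am and 9pm". The prompts do not mention the hormone sample. A daily video call, at an hour the participant schedules, covers drug-screen saliva testing and adverse events. Then: "Participants will also provide a saliva sample for hormone testing". On labelling the tube: "They will fill out the date and time and place in the freezer".
- **Adherence Monitoring.** "Participants will record themselves taking their morning and evening medication doses".
- **Study day 5.** "Participants will present to the ASD clinic by 10am for final study visit". The example timeline puts the home dose at 9:00, drug screens at 9:00, the timeline follow-back at 9:15, the hormone sample at 9:30 and cognitive testing at 9:35.
- **Analysis.** The Study Overview (D1) names progesterone level as a primary outcome. Statistical Analyses sets the Aim 1 level against the mid-luteal range using a mixed model with a random intercept. It names no day or time for that comparison and no term for time since dose.

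**The concern.** Aim 1 is partly a claim about a level, not only about a difference between arms. A level reached under twice-daily oral dosing has meaning only at a stated point in the dosing interval. If one woman gives her sample just before the 9am dose and another two hours after it, the first is near trough and the second may be near peak.

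Two things follow. The average over Days 2-5 mixes unknown points of the interval, so it is unclear what is being set against the mid-luteal range. The spread in timing also adds variance to the progesterone arm, which has only 20 women. A common sampling time cannot be recreated once the samples are taken.

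**Working it through.** **1. How many samples are affected.** There are four on-treatment samples per woman (Days 2, 3, 4 and 5), and three have no set time. In the progesterone arm that is 3 × 20 = 60 of 4 × 20 = 80 planned samples.

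**2. What the text allows.** With doses at 9am and 9pm, an untimed sample lies 0 to 12 h after the last dose. The D1 overview mentions concurrence with the adherence procedures, but the phrase attaches most naturally to the withdrawal ratings. Even if it covered the hormone sample, it would not say morning or evening, or before or after the dose.

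**3. Day 5.** The latest sample follows from arrival at 10:00 + 15 min drug screens + 15 min timeline follow-back = 10:30, which is 1.5 h after the dose. The example time of 9:30 gives 0.5 h. That lower end is nominal, because the home dose and the first clinic procedure are both listed at 9:00. Day 5 is thus bounded at about 0.5-1.5 h.

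**4. Possible size (illustration only).** The documents give no kinetics. Assume a one-compartment oral model at steady state with a 12 h interval:

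C(t) ∝ exp(−ke·t)/(1 − exp(−12ke)) − exp(−ka·t)/(1 − exp(−12ka)),

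where ke and ka equal ln 2 divided by the elimination and absorption half-lives. Assumed elimination half-lives are 3, 4, 8, 16 and 18 h, and absorption half-lives 0.5, 1 and 2 h (15 pairs). Sampling times are assumed to be spread evenly over the window.

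Example, elimination 4 h and absorption 1 h: ke = 0.1733, ka = 0.6931. The trough is 1/0.8750 − 1/0.9998 = 0.1426. The peak, at 2.41 h, is 0.7527 − 0.1882 = 0.5645. The ratio is 3.96.

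Sampling anywhere in 0-12 h, with values for absorption half-lives of 0.5, 1 and 2 h:

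| Elimination half-life | Highest/lowest level | CV from timing |
|---|---|---|
| 3 h | 9.44, 6.38, 3.43 | 62, 50, 33% |
| 4 h | 5.30, 3.96, 2.53 | 48, 39, 26% |
| 8 h | 2.27, 1.96, 1.58 | 25, 20, 13% |
| 16 h | 1.50, 1.39, 1.25 | 12, 10, 7% |
| 18 h | 1.43, 1.34, 1.22 | 11, 9, 6% |

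Fixed windows, range over the same 15 pairs:

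| Hours after dose | Highest/lowest level | CV |
|---|---|---|
| 11-12 (pre-dose) | 1.04-1.26 | 1-7% |
| 0.5-1.5 (matches Day 5) | 1.08-1.65 | 2-13% |

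Steady state does not describe Day 2. Using the two doses taken by then, with s(t) = exp(−ke·t) − exp(−ka·t) and C = s(t) + s(t + 12), the highest/lowest ratio over the daytime interval is 1.9 to 10.

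**5. What a fixed window does not remove.** Levels accumulate between Day 2 and Day 5. Pre-dose at 9am, Day 2 follows one dose and Day 5 follows seven, so the ratio is s(12) divided by the sum of s(12n) for n = 1 to 7. This is 0.86-0.94 for half-lives of 3-4 h and 0.38-0.42 for 16-18 h. At 1.5 h after the 9am dose (second against eighth dose) it is 0.95 to just under 1.00, and 0.50-0.64.

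**The case against.** The strongest reply has four parts.

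- **Levels are expected to be stable.** Both D2 and the Sample Size section say so. If the profile is nearly flat over 12 h, timing matters little; at assumed half-lives of 16-18 h the CV is only 6-12%. This stands as a limit on size. It is still an expectation, and the documents show no profile within the interval.
- **Timing is partly recoverable.** Tubes on Days 2-4 carry date and time, and doses are filmed. This stands, so it would be wrong to infer that sample times go unrecorded. The plan describes no use of these times, however, and adjusting afterwards is weaker than sampling at one time.
- **Even spread over 0-12 h is an assumption.** In the text the hormone sample follows the video call, and in practice many samples may cluster. This is fair. The protocol permits the full spread but does not predict it.
- **The study is a pilot.** Statistical Analyses calls every result preliminary, which lowers the weight. Yet feasibility of reaching luteal-like levels is Aim 1 itself.

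A reader might go further and infer that the comparison of arms is biased, or that samples would fall outside 2-20 ng/ml. The documents support neither. The same sampling rule applies to both randomised arms, and the withdrawal ratings have their own schedule. The 2-20 ng/ml range is not stated for saliva, and no kinetics are given to project against it.

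**Conclusion.** The gap is real and limited. No dose-relative time is set for the Days 2-4 hormone samples, and no sampling point is named for the Aim 1 comparison; the Day 5 sample is already bounded. The consequence is a noisier progesterone-arm level that is harder to interpret, not a biased trial.

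The size cannot be settled from the documents. The CV range of 6-62% rests wholly on the assumed half-lives, the one-compartment form and evenly spread sampling. The upper figures come from one corner of the grid (3 h elimination, 0.5 h absorption) and should not be read as an estimate. Priority is minor to moderate: the change is cheap, but it must be made before samples are collected.

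**What to change.** Set one dose-relative sampling window for Days 2-5 and name it in Statistical Analyses as the Aim 1 sampling point. Two workable options:

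1. **Pre-dose.** Sample at the existing 9am REDCap prompt, before the dose, on Days 2-5. The Day 5 tube is filled at home and brought in with the others. This describes trough levels.
2. **Post-dose.** Sample on Days 2-4 in a window after the 9am dose that matches the Day 5 clinic sample, about 0.5-1.5 h.

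Under either option, record actual dose and sample times on Days 2-5. Use time since dose as a sensitivity analysis within the progesterone arm only.

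Do not delay Day 5 cognitive testing to reach a later window. In the model above, moving it from 9:35 to 10:35 raises the level at testing from 59-90% to 88-100% of peak. Sedation is the most common adverse effect listed, and the move would also break the clock-time match with Day 1 testing at 9:35.

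**Cost.** Protocol wording, a dose-time field in the existing survey and a time on the Day 5 tube. Women have less freedom in when they give the home sample. Option 1 adds one home tube on Day 5; option 2 leaves a wider spread, because levels are still rising. Neither removes accumulation from Day 2 to Day 5, so results should also be shown by day. Sample size and randomisation are unchanged.

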#### Example study day 5 timeline

## D3. Instrumentation:

**Screening and Diagnostic Instruments.** *Quick Screen:* This assessment will be used to quickly determine whether an individual meets inclusion or exclusion criteria for study entry when they first present. The instrument is designed to assess for substance use and obvious psychiatric, medical, and logistic exclusions.

*Mini-International Neuropsychiatric Interview (M.I.N.I.):* The M.I.N.I. is a brief structured interview that was designed to assess current DSM-5 diagnoses (including lifetime mood disorder diagnoses) using a series of questions in dichotomous format (yes/no). Earlier studies have found that the M.I.N.I. is similar in sensitivity, specificity, and inter-rater reliability to other more lengthy diagnostic interviews, such as the SCID-I/P (Sheehan & Lecrubier, 2003; Sheehan et al., 1998). This instrument will be used to assess inclusionary/exclusionary psychiatric diagnoses.

**Substance-Related Instruments.** *Timeline Follow-Back:* Time Line Follow-back (TLFB; Sobell & Sobell, 1992) is a calendar-based instrument designed to assess daily substance use. Study subjects will be asked to estimate the amount of substance consumed with the aid of visual cues designed to accurately quantify consumption. Cannabis use will be recorded in unique sessions per day and quantity (grams) per session.

*Urine Drug Screening*: Drug screens will be performed using the One Step Multi-Drug Test Dip Card (Drugconfirm™), a lateral flow chromatographic immunoassay for the qualitative detection of drug or drug metabolite in the urine at the following cutoffs (ng/ml): cocaine (300), amphetamines (1000), methamphetamine (1000), THC (50), opiates (2000), and benzodiazepines (300). Samples will then be sent to MUSC laboratory for creatinine correction processing. Results will be used to ascertain abstinence prior to study procedures, cannabinoid levels, and to substantiate self-reports of all substance use.

Saliva Drug Screening: In addition to urine testing, participants will provide a saliva sample to verify abstinence from cannabis use through use of OraLab® testing (Varian, Inc.). This test is able to detect THC in saliva for up to 14 hours, which allows verification of abstinence in the past 12 hours as indicated in procedures.

Breathalyzer: To ascertain abstinence from alcohol prior to study visits, subjects will have their breath sampled for the presence of alcohol (Alco-Sensor III, Intoximeters Inc., St. Louis, MO)

Self-Report Instruments. The Positive and Negative Affect Scale – Expanded Form (PANAS-X; Watson & Clark, 1999) will be used to assess emotional states within the past few weeks. It is comprised of 60-item measure with two higher order dimensions (positive and negative affect) and 11 lower order subscales (e.g. guilt, hostility, sadness). Affective states are associated with relapse and therefore a baseline measure of affect is important to consider. The Cannabis Use Disorder Test-Revised (CUDIT-R; Adamson et al., 2010), will be used to assess cannabis use severity, and will be included as a covariate. The Frontal Systems Behavior Rating Scale (FrSBe; Grace & Malloy, 2001) will be used to measure behavioral syndromes associated with frontal lobe dysfunction. It consists of a total score and three subscale scores: apathy, disinhibition, and executive dysfunction, and has been used in substance-abusing populations as a selfreport assessment of cognitive functioning (Bickel et al., 2011) in conjunction with objective behavioral measures.

Assessments	Screening	Study day 1 visit	Study days 2-4 visits	Study day 5 visit
MINI	Х			
Breathalyzer, UDS	Х	Х		Х
Saliva (drug screen)	Х	Х	Х	Х
TLFB	Х	Х	Х	Х
FTND	Х			
Medication		Х	Х	Х
CWS (2x/day)		Х	Х	Х
Saliva (hormones)		Х	Х	Х
IC task		Х		Х
SDMT		Х		Х
AAT		Х		Х
FrSBe		Х		Х
CUDIT-R		Х		
PANAS		Х		

**Assessment Timeline** 

Participant Compensation. Participants will be compensated for participating in the study. Participants will receive \$40 for screening assessment (\$20 for interview and \$20 for physical exam) and \$50 for study days 1 and 5 visits. Participants will receive \$20 for each completion of medication adherence and CWS. Participants will receive an additional \$30 for each negative saliva cannabis drug screen and \$10 for a positive saliva screening on Days 2-4. Participants will receive \$10 for each salivary hormone sample collected on Days 2-4. Maximum potential compensation is \$420 value in the form of cash. Subjects will be compensated for negative drug screens since it is absolutely crucial to maintain abstinence in order to observe withdrawal symptoms.

Summary of compensation schedule:

	Screening	Day 1	Day 2	Day 3	Day 4	Day 5	
Attendance	\$40	\$50				\$50	
Medication/CWS		\$20	\$40	\$40	\$40	\$20	
Saliva Drug Screen			\$30	\$30	\$30		
Saliva Hormones			\$10	\$10	\$10		
Totals	\$40	\$70	\$80	\$80	\$80	\$70	\$420

**Confidentiality.** Confidentiality will be maintained using procedures that are employed as standard policy. Confidentiality of all research data will be maintained by keeping all data in a locked file. limiting access to the computer database to only study personnel, and by using patient code numbers/initials as opposed to names on all paperwork. Any requests for the release of patient information will be referred to [name].

**Data Management and Reduction.** All paper-based assessments (other than laboratory reports) will be entered into REDCap, a secure, web-based application designed exclusively to support data capture for research studies. REDCap provides an intuitive interface for data entry (with data validation), audit trails for tracking data manipulation, and automated export procedures for data downloading to statistical packages such as SPSS and SAS. Completed assessments will be entered within two weeks after the information has been collected from the subject. Quarterly database management and data integrity audits will be conducted.

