**Cannabis Abstinence.** Cannabis abstinence will be assessed using self-report, saliva drug testing, and cannabinoid levels. Self-report will be conducted using the TLFB (see *Instrumentation* section). Saliva drug testing will occur in person on Days 1 and 5, and participants will be trained to administer saliva screening. During days 2-4, participants will schedule a Skype/FaceTime call with study personnel and undergo drug screen procedures via teleconference. Cannabinoid levels will be assessed using urine toxicology collected on Days 1 and 5. Creatinine-corrected cannabinoid levels will be compared from Day 1 to Day 5 to confirm abstinence during the study period.

**Cognitive Testing.** The Symbol Digit Modalities Test (SDMT; Smith, 1982), Go/NoGo Inhibitory Control (IC) Task (Chikazoe et al., 2009), and Approach-Avoidance Task (Wiers et al., 2009) will be used to assess cognitive functioning. The SDMT measures sustained attention, response speed, and visuomotor coordination. It involves filling in a blank space below a symbol with the appropriate symbol-paired number as quickly as possible for 90 seconds. The main outcome is number of correct responses. A computerized IC task will be used to assess response inhibition. During the IC task, participants are instructed to press a button in response to common (75% of trials) and rare (12.5%) Go stimuli while inhibiting responding to rare NoGo stimuli (12.5%). The task provides errors of omission and reaction times during Go trials, and errors of commission on NoGo trials, and has been used in substance abusing populations (Froeliger et al., 2017). The AAT will be used to assess cannabis approach bias – a measure of implicit cognitive bias towards cannabis cues. During the AAT, participants are asked to respond to cannabis-related or neutral images by pushing or pulling a joystick based on an irrelevant image feature (i.e. border color). Primary outcome is cannabis approach bias, and a higher score indicates greater bias.

**Nicotine Dependence**: The *Fagerstrom Test for Nicotine Dependence (FTND; Heatherton, et al., 1991)* will be administered at screening to inform randomization procedures.

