#### **Potential Study Limitations**

Duration. Due to protracted nature of cannabis withdrawal, a longer study period would be ideal. However, given the pilot nature of this study the 5-day design should allow ample time for acute withdrawal symptoms to present, while maintaining adherence to the withdrawal protocol in a non-treatment seeking sample. Variable dosing. Since progesterone has not yet been tested in cannabis users, testing dose-related effects would provide more information as to efficacious dosing. Given numerous studies have used the proposed dose of 200mg bid in cocaine and nicotine dependent individuals, the proposed dose can be assumed to elicit the desired effect safely with confidence.

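### Payment for a negative cannabis screen stops after Day 4, so the night before the final withdrawal score and the only on-treatment cognitive tests carries no abstinence incentive

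*Combined protocol and SAP*

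**What the plan says.** The Participant Compensation paragraph, which follows the Assessment Timeline in section D3, pays $30 for each negative saliva cannabis screen and $10 "for a positive saliva screening on Days 2-4". The reason given is: "Subjects will be compensated for negative drug screens since it is absolutely crucial to maintain abstinence in order to observe withdrawal symptoms". In the compensation table the row "Saliva Drug Screen" shows $30 on each of Days 2, 3 and 4 and nothing on Day 5. The Day 5 total of $70 is $50 for attendance plus $20 for medication and CWS. Neither amount is said to depend on a screen result.

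A Day 5 screen is nevertheless planned. Section D2, Cannabis Abstinence, states: "Saliva drug testing will occur in person on Days 1 and 5". The Study day 5 visit text and the assessment table agree. On the home days, "participants will schedule a Skype/FaceTime call with study personnel and undergo drug screen procedures via teleconference", with no clock time fixed for the call.

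For the outcomes, section D2 says: "CWS will then be administered once on study days 1 and 5, and twice daily on study days 2-4". Respondents are asked to refer to the past 12 hours, and the example Day 5 timeline puts that score at 9am. Cognitive testing takes place only on Day 1, before the first dose, and on Day 5.

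**The concern.** The plan depends on payment to keep daily or near-daily users abstinent. Potential Study Limitations defends the 5-day length partly as a way of "maintaining adherence to the withdrawal protocol in a non-treatment seeking sample". Once the Day 4 call is over, a woman can use cannabis and lose no money. Leaving Day 1 unpaid makes sense, because abstinence only begins that day. No reason is given for leaving Day 5 unpaid.

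Women with the worst withdrawal have most reason to use that night, and use would be expected to relieve the symptoms being scored. If progesterone reduces withdrawal, such use would be more common on placebo, which would pull the Day 5 comparison toward no difference. The cognitive tests are meant to describe function during withdrawal, and some could be taken hours after use.

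**Working it through.** **1. Is the empty Day 5 cell a slip?** Adding the table by column, from screening to Day 5: 40 + 70 + 80 + 80 + 80 + 70 = $420, the stated maximum. With a $30 Day 5 screen, the Day 5 total is 70 + 30 = $100 and the maximum is 420 + 30 = $450. The stated maximum therefore holds only if the Day 5 screen is unpaid, and text and table agree.

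**2. Size of the incentive.** A positive screen still earns $10, so the amount at stake is 30 - 10 = $20 per screen. Over three days that is 3 × 20 = $60, and 60/420 = 14% of the maximum. None of it is tied to Day 5.

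**3. Length of the unpaid interval.** Assume the Day 4 call falls between 9am and 9pm. The time to 9am on Day 5 is then 24 h down to 12 h. In every case this contains the whole 12-hour recall window of the Day 5 CWS (9pm to 9am).

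**4. Outcomes exposed.** CWS scores after baseline: 1 (Day 1, 9pm) + 6 (Days 2-4) + 1 (Day 5) = 8. The Day 1 evening score coincides with the first dose, so 7 follow a dose. The Day 5 score is one of these 7. The Day 4 9pm score can also be affected if the call comes earlier that day. For cognition, the exposed session is 1 of 1.

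**5. Illustrative dilution.** The documents give no use rates or effect size, so these inputs are assumptions:
- W is the placebo withdrawal elevation without use, and the true reduction on progesterone is 30%.
- Women who use have their elevation fall to zero.
- The 7 post-dose scores are weighted equally, with a constant effect.

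Day 5 difference = (1 - placebo use) × W - (1 - active use) × 0.70W.
- 20% and 10% use: 0.80W - 0.90 × 0.70W = 0.17W, against 0.30W without use.
- 10% and 5% use: 0.90W - 0.95 × 0.70W = 0.235W.

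Averaged over the 7 scores:

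| Use (placebo / active) | Day 5 only affected | Day 4 9pm also affected |
|---|---|---|
| 20% / 10% | (6 × 0.30 + 0.17)/7 = 0.281W, loss 6% | (5 × 0.30 + 2 × 0.17)/7 = 0.263W, loss 12% |
| 10% / 5% | (6 × 0.30 + 0.235)/7 = 0.291W, loss 3% | (5 × 0.30 + 2 × 0.235)/7 = 0.281W, loss 6% |

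**6. Reach of a paid Day 5 screen.** Section D3, Saliva Drug Screening, gives detection for up to 14 hours. A screen at about 9am on Day 5 reaches back to about 7pm on Day 4. If the Day 4 call is at 9am, 24 - 14 = 10 of the unpaid hours stay outside the window. Use that lowers the 9pm score must come before 9pm, so only use between about 7pm and 9pm would be caught for that score.

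**The case against.** The strongest reply is that little of the primary evidence depends on Day 5. Withdrawal is collected repeatedly and analysed in a mixed model for repeated measures, no section makes Day 5 the primary time point, the cognitive aim is exploratory, and the Statistical Analyses section calls all results preliminary. This stands, and it limits the weight of the point.

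A second reply is that detection continues. Day 5 has an in-person saliva screen, urine toxicology and the Timeline Follow-Back (TLFB), and creatinine-corrected cannabinoid levels are compared between Days 1 and 5. This also stands: what lapses is the payment, not the check. But detection does not deter use, the analysis section gives no rule for data from women who used, and a compromised Day 5 cognitive session cannot be repeated.

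Third, the payment structure has a logic: screens and hormone samples are paid separately on home days, while clinic days carry a $50 attendance fee. That may explain the layout, but it still leaves Day 5 without a contingency.

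Finally, the illustration treats all late use as if payment would have prevented it, and lets symptoms fall to zero. The documents give no evidence on what $20 prevents. The percentages are therefore upper values for the assumed use rates.

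**Conclusion.** The gap is real and certain as a matter of payment: the final night has no abstinence incentive, contrary to the plan's own rationale. It leaves the 9am Day 5 CWS and all on-treatment cognitive testing less protected than the scores on the paid days.

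For the primary withdrawal outcome the likely effect is small: about 3-6% of the average treatment difference if only the Day 5 score is affected, and 6-12% if the Day 4 9pm score is too. These figures rest on the assumed use rates, a 30% true effect, complete symptom relief after use and equal weights. The effect on cognition cannot be quantified from the documents.

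A reader might infer that the incentive lapses just before the trial's endpoint and that 43% (0.13/0.30) or 22% (0.065/0.30) of the treatment effect is lost. The documents do not support this: those losses belong to the Day 5 difference alone, under assumed inputs, and Day 5 is one of 7 post-dose scores. Nor do they support the inference that late use would go unseen. This is an inexpensive improvement and does not threaten the validity of the trial.

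**What to change.** In the Participant Compensation paragraph and its table, pay the Day 5 in-person saliva screen on the same terms as Days 2-4 ($30 negative, $10 positive). Restate the Day 5 total as $100 and the maximum as $450. Tell participants during the Day 1 instructions that the Day 5 result counts for payment.

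The cost is at most 30 × 40 = $1,200, plus a short amendment and consent update. No new procedure is needed, because the screen is already performed. Given the 14-hour detection limit, the change mainly protects the Day 5 CWS and the cognitive tests. It does little for the Day 4 9pm score, and the amendment should not claim otherwise.
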